### 7.1.1 Molecular pre-screening

All participants entering the pre-screening phase must sign the molecular pre-screening informed consent form (ICF).

#### Activating mutations L858R and ex19del

For participants in Phase Ib part and Phase II part Groups 1, 3, 4 and 5 local pathology reports showing L858R and/or ex19del evidence must be available in medical records prior to sign the main ICF. Documented proof of other rare activating mutations that confer sensitivity to first and second generation EGFR inhibitors (e.g. L861Q, G719X, S768I) also satisfies eligibility criteria.

For Phase II Group 2 (de novo EGFR T790M mutation), local pathology reports showing the activating mutation analysis results must be available in the medical records as well. The participants will be enrolled irrespective of the activating mutation status, i.e. may harbor or may not harbor an EGFR activating mutation in addition to the EGFR T790M mutation.

Activating mutation status as per local pathology reports must be recorded in the eCRF for all participants.

#### Resistance mechanisms EGFRT790M and MET dysregulation: Phase Ib

In Phase Ib, if mutational status for EGFRT790M and MET pathway dysregulation are unknown following treatment with EGFR-TKI, a newly obtained tumor sample (preferred) or an archival tumor sample collected at or following progression on prior EGFR TKI therapy, should be provided to Novartis designated central laboratory for EGFR mutation and MET dysregulation testing.

In Phase Ib, acceptable local test results for EGFRT790M should be assessed using:

- In the United States with QIAGEN Therascreen EGFR test,
- In the other countries with either Roche COBAS or QIAGEN Therascreen EGFR test.

MET dysregulation should be preferably analyzed by FISH, and if sufficient tumor material is available additionally by IHC.

MET dysregulation is defined as either

- IHC 3+ (defined as  $\geq 50\%$  of cells staining with high intensity) and/or
- MET gene copy number  $\geq 4$

For Group 5: MET amplified is defined as gene copy number  $\geq 5$

For Phase Ib part, the participant will be able to proceed with study specific screening procedures if either

- Activating mutations L858R and/or ex19del are documented locally AND the central laboratory confirms that sufficient tumor sample has been received to perform the EGFRT790M mutation and/or MET dysregulation testing or

- Activating mutations L858R and/or ex19del are documented locally AND EGFRT790M mutational and MET statuses have been determined by the appropriate analysis methods at the local laboratory.

### **Resistance mechanisms EGFRT790M and MET dysregulation: Phase II**

All participants must have sufficient tumor samples (newly obtained or archival) available for EGFRT790M and MET statuses determination by Novartis designated central laboratory on a biopsy collected:

- At or any time after progression on prior line of EGFR TKI for Group 1 (EGFRmut, any T790M, any MET, 2/4L antineoplastic, EGFR TKI resistant);
- At any time for Group 2 (EGFRmut, de novo T790M, any MET, 1/3L antineoplastic, EGFR TKI naïve) and Group 3 (EGFRmut, T790M negative, any MET, 1L antineoplastic);
- At any time in treatment-naïve participants or at/or any time after progression on the last treatment line for advanced disease for Group 4 (EGFRmut, any T790M, any MET, 1L (treatment naïve) 2-3L antineoplastic); if biopsy is not available after last treatment, the most recent available archival biopsy should be provided;
- At or any time after progression on prior line of EGFR TKI for Group 5 (EGFRmut, T790M-, MET GCN $\geq$ 5, 2L, EGFR TKI resistant).

Participants in Phase II will be able to proceed with main informed consent form signature and study specific screening procedures if activating mutations L858R and/or ex19del analysis results are documented locally AND sufficient tumor samples have been submitted to the central laboratory for EGFRT790M and MET statuses determination.

In the Phase II, MET dysregulation is defined as either:

- IHC 3+ (defined as  $\geq$ 50% of cells staining with high intensity) and/or
- MET gene copy number  $\geq$  4

In Phase II Group 5, MET amplified is defined as MET gene copy number (GCN)  $\geq$  5.

Note: Participants with prior documentation of EGFR mutation and/or MET dysregulation testing from the Novartis designated central laboratory using the same prescreening tests used in this protocol (i.e. being re-prescreened or coming from another Novartis study) are potentially eligible. Repeat tumor biopsy or additional archival tumor may not be required for these participants provided the central laboratory confirms adequate tumor tissue remains for the required study analyses.

However, if there is not enough residual tissue at the central laboratory to perform all required study analyses additional material from an archival tumor biopsy (preferably the same) will be requested.

In Phase II Group 5, MET amplification (GCN $\geq$ 5) status can be determined per local laboratory result (see [Section 5.2](#)) as long as an adequate amount of tumor tissue (archived or if not available, newly obtained biopsy sample) is available at the time of enrollment for submission for retrospective central assessment of MET gene amplification status using a validated FISH test at the Novartis-designated laboratory. MET amplification testing by FISH is preferred and results from other tissue-based molecular testing methods, such as next generation sequencing

(NGS) or PCR, are accepted. Blood-based results and IHC results are not acceptable for determining MET amplification with  $GCN \geq 5$ . If a local result is not available, a tumor tissue sample must be submitted during pre-screening and determined as MET amplified ( $GCN \geq 5$ ) per central Novartis-designated laboratory.

MET testing may be performed while participants are still receiving anti-cancer therapy. However, the participant can only be screened for the main study once he/she has discontinued the last prior systemic treatment due to disease progression.

### 7.1.2 Screening

The study IRB/IEC approved main ICF must be signed and dated before any screening procedures are performed.

For all participants (except Phase II Group 5), an archival or newly obtained tumor biopsy sample will be required to be submitted to a Novartis central laboratory for genetic alterations assessment at baseline (Next Generation Sequencing [NGS] assay).

In addition, a mandatory blood sample will be collected from all participants (except Phase II Group 5), during the screening phase (or at the latest on Cycle 1 Day 1 before first study drug administration). This will be used to isolate cfDNA for assessment of EGFR mutation status.

Participants will be evaluated against study inclusion and exclusion criteria and safety assessments. For details of assessments, refer to [Table 7-1](#) and [Table 7-2](#). Screening assessments must be repeated if performed outside of the specified screening windows (refer to [Section 7.1](#)).

The main screening period commences as soon as the participant signs the main ICF and ends when the participant fails screening or starts treatment. Evaluations will be performed within 4 weeks (i.e. within 28 calendar days) prior to the first dose of study drug, unless otherwise noted. All screening assessments, including laboratory assessments, must be performed as described in the protocol ([Table 7-1](#) and [Table 7-2](#)). Any imaging assessments already completed as participant's standard of care within 28 days prior to start of treatment, including before signing the main study ICF, can be considered as the baseline images for this study. Any imaging assessments obtained after first dose cannot be considered baseline images.

### Screening for hepatitis B

Prior to study entry, all participants must be screened with HBV serologic markers: HBsAg, HBsAb, and HBcAb. Check HBV-DNA if HBsAg and/or HBcAb are positive. Refer to [Table 6-10](#) for actions to be taken based on screening HBV results.

### Screening for hepatitis C

Screen all participants for HC Ab. If HC Ab is detected then check HCV-RNA. Only participants who are HC Ab negative or HC Ab positive with an undetectable level of RNA are eligible to be enrolled. Note: participants with detectable HCV-RNA will not be eligible for the study. Participants with HCV-Ab positive or history of hepatitis C infection should be monitored every 8 weeks (or more frequently if clinically indicated) with HCV-RNA.

All screening evaluations will be performed within 28 days prior to Treatment Day 1. HBV/HCV tests will be performed by a local laboratory for the Phase Ib part and by a central laboratory for the Phase II part. HBV/HCV test results should be available prior to the first dose of study treatment (capmatinib + nazartinib). Participants with positive baseline hepatitis B results have to start antiviral treatment 1 to 2 weeks prior to the first dose of study treatment (capmatinib + nazartinib) and need to be monitored with HBV-DNA every 4 weeks (or more frequently if clinically indicated). Participants with HC Ab positive or history of hepatitis C infection should be monitored every 8 weeks (or more frequently if clinically indicated) with HCV-RNA.

### **Eligibility Check**

For participants enrolled in the Phase II part of the study, once all screening procedures are completed, an eligibility checklist must be completed via IRT by the investigator or designee prior to receiving the first dose of study treatment. Please refer to and comply with the detailed guidelines in the IRT manual.

After the eligibility has been checked and confirmed that the participant is eligible for the trial, then the participant can be enrolled into the study.

A participant who has a laboratory test result or an ECG finding that does not satisfy the entrance criteria may have the test(s) repeated. These test(s) may be repeated as soon as the investigator believes the re-test result(s) is/are likely to be within the acceptable range to satisfy the entrance criteria. If re-tests are performed during the 28-days screening period, the participant will not be required to sign another ICF, and the original participant ID number assigned by the investigator will be used. In the event that the laboratory test(s) cannot be performed during the original screening period of 28 days, or the re-test(s) do not meet the entrance criteria, or other eligibility criteria have changed and are not met anymore, the participant is considered a screen failure, and must be discontinued from the study. Participants who met all eligibility criteria but fail to be started on treatment as scheduled may also be re-screened, provided the participant was not registered previously in the CRF as having entered the Treatment Period.

A new ICF will need to be signed if the investigator chooses to re-screen the participant after a participant has screen failed.

All required screening activities must be performed when the participant is re-screened for participation in the study. An individual participant may only be re-screened once for the study.

Once the number of participants screened and enrolled is likely to ensure target enrollment, the Sponsor may close the study to further screening. In this case, the participants who screen failed will not be permitted to re-screen.

If a participant fails screening but is re-screened, the participant must be re-screened using the same participant number.

All eligibility criteria must be re-checked, based on the most recent data available, and met prior to enrollment of the participant into the study.

If the re-screening is successful, the following information should be collected in the CRF:

- Date the study informed consent was first signed.
- All assessments done during the first screening period.
- All assessments repeated during the re-screening period (e.g. ECG, lab).
- Updated information as per latest status during the re-screening period e.g. Medical history, diagnosis and extent of cancer.
- Adverse events based on the date of re-consent.

#### **7.1.2.1 Information to be collected on screening failures**

Participants who sign the molecular pre-screening ICF, or the molecular pre-screening ICF and the main ICF, but fail to be started on study treatment for any reason will be considered a screen failure.

The reason for molecular pre-screening failure or screening failure will be entered on the Screening Phase Disposition Page.

For all participants except participants in Phase II Group 5, the demographic information, informed consent, and Inclusion/Exclusion pages must also be completed for Screen Failure participants.

For participants in Phase II Group 5 the following eCRF pages must be completed for screening failure participants:

- EGFR and T790M status as per participant's record
- Information on prior local testing for MET amplification status (if available)
- Tumor samples collection (archival or newly obtained) for central confirmation of MET amplification status and T790M status (if local T790M status is not available)
- NSCLC diagnosis and extent of disease
- Date of diagnosis and stage of NSCLC
- Site of active disease
- Characteristics of disease
- Screening phase disposition
- Demography
- Informed consent
- Inclusion/Exclusion Criteria
- Withdrawal of consent (if applicable)
- Death (if applicable)

No other data will be entered into the clinical database for participants who are screen failures, unless the participant experienced a SAE during the Screening Phase (see [Section 8](#) for SAE reporting details). For molecular pre-screening failures, only SAEs possibly related to a study procedure will be reported.

### 7.1.2.2 Participant demographics and other baseline characteristics

Data to be collected will include general participant demographics, relevant medical history and current medical conditions, diagnosis and extent of tumor, details of prior anti-neoplastic treatments, HBV and HCV status, and any other assessments that are done for the purpose of determining eligibility for inclusion in the study. All medications and significant non-drug therapies (including herbal medicines, physical therapy and blood transfusions) taken within 4 weeks prior to first dose of study drug must be recorded on the eCRF. Smoking history will be recorded on the eCRF at screening.

### 7.1.3 Treatment period

A treatment cycle is defined as 28 days (4 calendar weeks) for the purposes of scheduling procedures and evaluations. Please refer to [Table 7-1](#) and [Table 7-2](#) for details of the timing of required assessments and [Section 7.1](#) for visit windows.

Participants will be treated until participant experiences unacceptable toxicity, progressive disease and/or treatment is discontinued at the discretion of the investigator or withdrawal of consent/opposition to use data/biological samples as described in [Section 7.1.5](#).

### 7.1.4 Discontinuation from study treatment and from study

Participants may voluntarily discontinue from the study treatment for any reason at any time. If a participant decides to discontinue from the study treatment, the investigator should make a reasonable effort (e.g. telephone, e-mail, letter) to understand the primary reason for this decision and record this information in the participant's chart and on the appropriate CRF pages. They may be considered withdrawn/opposition to use data/biological samples, if they state an intention to withdraw/opposition to use data/biological samples, fail to return for visits, or become lost to follow-up for any other reason.

The investigator must discontinue study treatment for a given participant if he/she believes that continuation would be detrimental to the participant's well-being.

Discontinuation from study treatment is required under the following circumstances:

- Adverse events and laboratory abnormalities meeting criteria for study treatment discontinuation: refer to [Section 6.3](#).
- Pregnancy
- Interruption of one of the study drugs for 21 consecutive days or more, regardless of reason for study drug interruption
- Use of prohibited treatment, refer to [Appendix 4](#).
- Any other protocol deviation that results in a significant risk to the participant's safety.

Participants who discontinue from study treatment agree to return for the end of treatment and follow-up visits indicated in the Assessment Schedule (refer [Section 7](#)). In addition, before a new anti-neoplastic therapy is initiated for a participant, it is strongly recommended to perform a tumor assessment. If they fail to return for these assessments for unknown reasons, every effort (e.g. telephone, email, letter) should be made to contact them as specified in [Section 7.1.7](#).

For Phase II, the investigator must also contact the IRT to register the participant's discontinuation from study treatment.

Discontinuation from study is when the participant permanently stops receiving the study treatment, and further protocol-required assessments or follow-up, for any reason.

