#### **7.1.5 Withdrawal of informed consent/Opposition to use data/biological samples**

Participants may voluntarily withdraw consent to participate in the study/make opposition to use data/biological samples for any reason at any time.

Withdrawal of consent/opposition to use data/biological samples occurs when a participant:

- explicitly requests to stop use of their biological samples and/or data (opposition to use participant's data and biological samples)

and

- no longer wishes to receive study treatment

and

- does not want any further visits or assessments (including further study-related contacts).

This request should be in writing (depending on local regulations) and recorded in the source documentation.

Novartis will continue to retain and use all research results (data) that have already been collected for the study evaluation, including processing of biological samples that has already started at time of consent withdrawal/opposition. No new Personal Data (including biological samples) will be collected following consent withdrawal/opposition. If a participant withdraws consent, the investigator should make a reasonable effort (e.g. telephone, e-mail, letter) to understand the primary reason for this decision and record this information.

Where consent to the use of Personal and Coded data is not required in a certain country's legal framework, the participant therefore cannot withdraw consent. However, they still retain the right to object to the further collection or use of their Personal Data.

Study treatment must be discontinued and no further assessments conducted and the data that would have been collected at subsequent visits will be considered missing.

Further attempts to contact the participant are not allowed unless safety findings require communication or follow up.

If the participant agrees, a final evaluation at the time of the participant's consent withdrawal/opposition should be made as detailed in the assessment table (refer to [Section 7](#)).

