#### **Survival follow-up**

Upon completion of the 30-day follow-up or disease progression follow-up, all participants except those who withdrew consent for follow-up as a result of participant decision, or were lost to follow-up, will be followed for survival every 3 months (telephone call) until death or until the end of the study (Last Patient Last Visit, see [Section 4.3](#)). Participant's survival status may be collected via a phone call.

This visit does not apply for participants in Phase II Group 5.

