### **7.1.7 Lost to follow-up**

For participants whose status is unclear because they fail to appear for study visits without stating an intention to discontinue from study treatment or discontinue from study or withdraw

consent /oppose to the use of their data/biological samples, the investigator should show "due diligence" by contacting the participant, family or family physician as agreed in the informed consent and by documenting in the source documents steps taken to contact the participant, e.g., dates of telephone calls, registered letters, etc. A participant should not be considered lost to follow-up until due diligence has been completed. Participants lost to follow-up should be recorded as such on the appropriate Disposition eCRF.

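### Section 7.1.4 permits silent non-attenders to be classed as withdrawn or opposed to data use, contradicting the definition in 7.1.5 and the tracing duty in 7.1.7

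*Protocol*

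**What the plan says.** Section 7.1.4 describes participants who stop study treatment and then assigns a status: "They may be considered withdrawn/opposition to use data/biological samples, if they state an intention to withdraw/opposition to use data/biological samples". The same sentence adds two alternatives to a stated intention: that they "fail to return for visits, or become lost to follow-up for any other reason". Further down, the same section gives another instruction for people who stop coming: "If they fail to return for these assessments for unknown reasons, every effort (e.g. telephone, email, letter) should be made to contact them", with a pointer to 7.1.7.

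Section 7.1.5 defines withdrawal/opposition by three conditions joined by *and*. The participant "explicitly requests to stop use of their biological samples and/or data", wants no more study treatment, and wants no further visits, assessments or contact. The consequences are that treatment stops, "no further assessments conducted and the data that would have been collected at subsequent visits will be considered missing", and "Further attempts to contact the participant are not allowed unless safety findings require communication or follow up".

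Section 7.1.7 covers participants who stop appearing without announcing that they are discontinuing, withdrawing or objecting. The site must try to reach them, their relatives or their family doctor, and must document the attempts. "A participant should not be considered lost to follow-up until due diligence has been completed", and the disposition page must then show that status.

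Under 7.1.6, tumor follow-up after treatment ends for those who withdrew or were lost. Survival calls cover "all participants except those who withdrew consent for follow-up as a result of participant decision, or were lost to follow-up", and do not apply to Group 5.

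**The concern.** One silent non-attender can fall under two incompatible instructions. Under 7.1.7 the site must look for the person and, failing that, record a loss to follow-up. Under the extra clause in 7.1.4 the site may record withdrawal/opposition instead, and 7.1.5 attaches a contact ban to that status.

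The people at stake are those who have missed visits and could still be traced. If they are coded as objectors, routine collection of safety, tumor and survival information on them can end. In advanced lung cancer it is plausible, though the protocol does not say so, that some people stop attending because they are getting worse or tolerating treatment badly. Follow-up would then be lost in a way related to outcome. The record would also show an objection to data use that the participant never made. None of this can be repaired at the analysis stage, because information that was never sought cannot be recovered.

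**Working it through.** No sample size, power or event figure is involved, so the check is a comparison of the sections.

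**1. Who qualifies as withdrawn/opposed?**
- 7.1.4: a stated intention, *or* missed visits, *or* loss to follow-up.
- 7.1.5: an explicit request *and* refusal of treatment *and* refusal of further visits or contact.
- A missed visit without a statement meets the 7.1.4 test and none of the three 7.1.5 conditions. Both sections use the same term for the status, so they contradict each other.

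**2. What must the site do about a silent non-attender?**
- 7.1.7 and the later sentence of 7.1.4: make contact attempts. Section 14.1.4.2 repeats the due-diligence duty.
- 7.1.5, if the withdrawn/opposed status is applied: no contact unless safety findings require it.
- 7.1.4 therefore also conflicts with itself.

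**3. Which follow-up ends?**
- 7.1.6 removes withdrawn/opposed participants from the 8-weekly tumor assessments.
- The 3-monthly survival calls exclude those who withdrew by their own decision. A silent non-attender made no such decision, so the label fits badly, but a site that has coded withdrawal has a ready reason to stop calling. This concerns Phase Ib and Groups 1 to 4 only.
- The 30-day safety contact is required of all participants in 7.1.6, but 7.1.5 stops assessments and contact once the status is assigned.

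**4. Which analyses are exposed?**
- OS (10.7.2.1): withdrawn and lost participants are censored at the date of last contact.
- PFS and duration of response (10.7.2.1): without an event, censoring is at the last adequate tumor assessment. PFS events found after two or more missing tumor evaluations are also censored there, so tracing recovers a PFS event only if it happens early.
- ORR, primary in Groups 1 to 3 (10.5.3): a missing best overall response counts as treatment failure, so lost information does not raise the response rate.
- Censoring reasons (14.1.4.5.6): loss to follow-up and withdrawn consent are separate categories for PFS. The 7.1.4 clause blurs them.

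**5. Direction.** If non-attenders are doing worse than those who stay, censoring them tends to overstate OS, PFS and duration of response. If non-attendance is unrelated to outcome, the loss costs precision and does not bias the estimates.

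**The case against.** The best defense is that the clause is loose wording surrounded by clear rules. It says participants *may* be so considered. It follows a sentence about people who have decided to stop treatment, so it may not be meant for every non-attender. Section 7.1.5 asks for the request to be recorded in source documents, and in writing where local rules require, which a silent participant cannot satisfy. Section 7.1.7 addresses exactly this person. Section 9.1 adds that, even when authorization to use health information is revoked, permission for safety follow-up should be sought. The code by itself also changes no censoring: OS treats withdrawn and lost participants alike, and both leave tumor follow-up. PFS and OS are secondary, single-arm descriptions.

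Most of this stands as a limit on the consequences. It does not remove the contradiction. On the narrow reading, those who have stopped treatment are still expected back for end-of-treatment and follow-up visits, and 7.1.4 itself orders that they be contacted if they do not return.

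Three stronger readings should be resisted:
- A reader might infer that the site *must* stop looking. The text permits the classification and does not compel it, and the contact ban has a safety exception.
- A reader might infer that data *are* lost selectively. They can be lost. Whether they are depends on how sites use the clause and why people stop attending.
- A reader might infer that PFS and OS are both censored at last contact. That is the rule for OS only.

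**Conclusion.** The contradiction is real and rests on the text alone. Section 7.1.4 permits a status that 7.1.5 does not allow for a silent non-attender and that defeats the tracing required by 7.1.7. The avoidable loss is confined to participants who missed visits, could still have been found, and were coded as withdrawn/opposed. Those declared lost after genuine due diligence leave follow-up in any case.

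The claim of informative censoring for OS, PFS and duration of response assumes that non-attendance is related to deterioration. The size cannot be derived: the protocol text at hand states no expected rate of missed visits, loss or withdrawal. A reader might try a bound. An assumed 5% to 15% of 40 is 2 to 6 participants, and 4 unknown out of 40 gives 4/40 = 10 percentage points between all alive and all dead at a landmark. Neither the rate nor the span has support in the protocol. The span also supposes that all four were miscoded, none was traced, and all would otherwise have been found, so it should not be read as the effect of the clause.

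The correction is still worth making, because the clause governs site conduct and consent status.

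**What to change.** In the withdrawal/opposition sentence of 7.1.4, delete "fail to return for visits, or become lost to follow-up for any other reason". Have the sentence refer to 7.1.5 for the definition of the status, so that it is recorded only when all three conditions there are met. State that unexplained non-attendance is handled only under 7.1.7 and is recorded as lost to follow-up once due diligence is complete.

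The cost is one edited sentence in a protocol amendment and a matching instruction for the disposition page. No visits or contacts are added, because 7.1.7 already requires the tracing.
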